8. Medical conditions that are occurring concomitantly at Visit 1 will be recorded as baseline conditions in the electronic Case Report Form eCRF.
9. Measurements of vital signs should precede blood sampling, [REDACTED]
10. At each time point, height and sitting height will be assessed three times and each assessment will be recorded into the patient's files and transcribed into the eCRF. An average of the 3 measurements will be calculated.
For new patients who didn't previously participate in InPedILD®: height and weight assessed in the 2 years prior to screening (Visit 1) will also be collected, if available.
11. Electrocardiogram (ECG) at rest (if possible, prior to blood sampling) will be performed at Visit 1 and at visits specified in the [Flow Chart](#) thereafter (every 24 weeks).
For new patients, it will be repeated at Visit 2 prior to treatment allocation only if abnormal at Visit 1.
12. **For new patients,** the safety laboratory tests of Visit 1 must be repeated if interval between Visit 1 and Visit 2 is longer than 6 weeks.
13. Pregnancy testing should be conducted in all female patients, even pre-menarche, every 4 weeks. Pregnancy blood test will be conducted at each scheduled visit until EoT. At the Follow-up/EoS Visit, the pregnancy test will be conducted on urines (if acceptable). Additionally, urine pregnancy test should be repeated at home or at a local laboratory / local doctor, every 4-6 weeks if applicable, between clinic visits until the end of the trial. If urine test is not acceptable to local authorities, a blood test will be done at a local laboratory. In case of premature treatment discontinuation, when patient continues with visits off treatment, the pregnancy tests at home (for female patients) are only required to be continued every 4 weeks for the 3 months after last trial drug intake.

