From Visit 2 for roll-over patients ≥ 26 weeks and from Visit 3 for new patients and for roll-over patients < 26 weeks, urine dipstick pregnancy tests will be provided with pregnancy test diary card when needed. Use of pregnancy test diary card will be explained with the patient / parent(s)/legal guardian and training will be repeated as needed. The pregnancy test diary card will be used to support the record of the date and result of test(s) between consecutive visits. Pregnancy test diary card will be reviewed at clinic visits. In case a positive test is reported the sponsor should be contacted immediately. Refer to [Section 3.3.4.1](#) for further instructions. Refer to [Section 5.2.7.2.3](#) for detailed information on event reporting in case of pregnancy.
14. [REDACTED]
15. **For new patients:** Order of lung function measurements: 1. FVC followed by patient's rest; 2. DLCO.
For roll-over patients, DLCO not applicable.
For all patients: after Visit 2 FVC measurements to be done at the same time each visit (+/- 90 min), with reference time at Visit 2.
16. [REDACTED]
17. Interactive Response Technology (IRT) should be notified upon obtaining informed consent.

18.

Please refer to [Appendix 10.1](#) for details.

19.

20.

21. Bone imaging. Please refer to [Section 5.2.5](#) and to the image acquisition guideline available in the ISF for details. For patients aged 19 and older, please see additional information at the end of the footnote.

For new patients: Bone imaging is required for all new patients who qualified for assignment of nintedanib treatment at Visit 2 as baseline. If it's not possible to conduct the baseline bone imaging at Visit 2, the procedure can be done in the 2 weeks immediately after the visit (until D15).

Imaging follow-up will be conducted only in patients with open physes at predefined time points. Imaging follow-up will be conducted, if applicable, at 12 weeks, 24 weeks, 36 weeks, 52 weeks, 76 weeks, 104 weeks, 128 weeks, 156 weeks, and every 24 weeks thereafter until the end of study or closure of the physes. If it's not possible to conduct the follow-up at the predefined time points, the procedure can be done within 1 week before and after this time point with always minimum of 10 weeks (during the first year)/22 weeks (thereafter) and always maximum of 16 weeks (during the first year)/28 weeks (thereafter) between 2 procedures.

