3.3.3 Exclusion criteria

For new patients:

1. AST and/or ALT >1.5 x ULN at Visit 1.
2. Bilirubin >1.5 x ULN at Visit 1.
3. Estimated Glomerular Filtration Rate (eGFR) <30 mL/min/1.73m² at Visit 1 (please refer to [Appendix 10.3](#)).

[Note: Laboratory parameters from Visit 1 have to satisfy the laboratory threshold values as shown above. Visit 2 laboratory results will be available only after the visit In case, at Visit 2, the results do no longer satisfy the entry criteria, the Investigator has to

decide whether it is justified that the patient remains on study drug. The justification for decision needs to be documented. Laboratory parameters that are found to be abnormal at Visit 1 are allowed to be re-tested (once) if it is thought to be a measurement error (i.e. there was no abnormal result of this test in the recent history of the patient and there is no related clinical sign) or the result of a temporary and reversible medical condition, once that condition is resolved.]

4. Patients with underlying chronic liver disease (Child Pugh A, B or C hepatic impairment) at Visit 1.
5. Other investigational therapy received within 1 month or 5 half-lives (whichever is shorter but ≥ 1 week) prior to Visit 2 except investigational therapy received in InPedILD[®] trial.
6. Significant pulmonary arterial hypertension (PAH) defined by any of the following:
 - a. Previous clinical or echocardiographic evidence of significant right heart failure
 - b. History of right heart catheterization showing a cardiac index ≤ 2 l/min/m²
 - c. PAH requiring parenteral therapy with epoprostenol/treprostinil
7. In the opinion of the Investigator, other clinically significant pulmonary abnormalities.
8. Cardiovascular diseases, any of the following:
 - a. Severe hypertension, uncontrolled under treatment, within 6 months of Visit 1.
Uncontrolled hypertension is defined as
 - i. In children 6 to ≤ 12 years old: ≥ 95 th percentile + 12 mm Hg or $\geq 140/90$ mm Hg (whichever is lower) (systolic or diastolic blood pressure equal to or greater than the calculated target value) (please refer to [Appendix 10.5](#)). Not applicable in France.
 - ii. In adolescents 13 to 17 years old: systolic blood pressure ≥ 140 mm Hg or diastolic blood pressure ≥ 90 mm Hg (please refer to [Appendix 10.5](#)). In France, applicable for adolescents 12 to 17 years old.
 - b. Myocardial infarction within 6 months of Visit 1
 - c. Unstable cardiac angina within 6 months of Visit 1

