4.1.4 Drug assignment and administration of doses for each patient

For an individual patient, the start of treatment period will be planned at Visit 2, and the end of treatment period is planned at the EoT Visit. The first dose of trial medication should be taken during the Visit 2 in the morning at the clinic and the last dose of trial medication should be taken in the evening before the EoT Visit.

During the treatment period, the treatment for an individual patient will be assigned via IRT contact during scheduled clinic visits detailed in the [Flow Chart](#).

Each patient will receive active drug at dosage of 150 mg bid, 100 mg bid, 75 mg bid, 50 mg bid or 25 mg bid. Nintedanib will be administered orally on a twice daily basis.

Based on the assigned dose, including possible dose reduction, the daily dose of trial medication will consist of 1 capsule (150 mg, 100 mg, or 25 mg strength) or 2 capsules (25 mg strength), or 3 capsules (25 mg strength) to be taken per os twice daily (b.i.d.) (see [Table 4.1.2: 1](#)).

Patients not able to swallow the 150 mg strength or the 100 mg strength capsule will have the possibility to take the 25 mg strength capsules (6 or 4 capsules per dose, respectively). To obtain kits with smaller capsules, an unscheduled visit should be registered in IRT.

At each concerned visit, the number of dispensed wallets will be adapted to assure sufficient coverage until the next dispensing visit.

The investigational product should only be dispensed to parents/caregiver(s) (or patients if applicable based on their maturity) by authorized personnel as documented in the "Trial Staff List".

In the event of force majeure or other disrupting circumstances (e.g. pandemic, war, please see [Section 6.1](#)), physical patient visits to the sites may not be feasible or may need to be restricted to ensure patient safety. Based on a thorough assessment of the benefits and risks,

the investigator may still decide to continue trial treatment. Where permitted by local law and regulations, trial medication may be shipped directly to the patients' home. If the defined minimum frequency of trial procedures cannot be adhered to, discontinuation from trial medication should be considered. (see [Appendix 10.9](#) for details).

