5.2.3 Safety laboratory parameters

Safety laboratory parameters to be assessed at scheduled visits are listed in [Table 5.2.3:1](#). For the sampling time points please see the [Flow Chart](#).

All analyses will be performed by a central laboratory, the respective reference ranges will be provided in the ISF.

The eGFR will be calculated based on serum creatinine according to Schwartz formula [[R10-0828](#), [R11-4789](#)] in adolescent and according to CKD/EPI formula in adults [[R12-1392](#)] (see [Appendix 10.3](#))

Patients do not have to be fasted for the blood sampling for the safety laboratory.

Blood sampling will be conducted using materials and techniques suitable for the paediatric population. Venous whole blood will be collected in appropriate syringes provided by the sponsor through the assigned central laboratory. All efforts should be made to use the lowest amount of blood per sample as technically possible, e.g. by using special paediatric collection systems.

Instructions regarding sample collection, sample handling / processing and sample shipping are provided in the Laboratory Manual in the ISF.

The central laboratory will send reports to the investigator. It is the responsibility of the investigator to evaluate the laboratory reports. Clinically relevant abnormal findings as judged by the investigator will be reported as adverse events (please refer to [Section 5.2.7](#)).

Overall, approximately 6.1 mL blood will be taken for standard safety laboratory tests at each scheduled visit during the trial.

Pregnancy tests

During the treatment period and the follow-up period a pregnancy test must be conducted in all female patients every 4 weeks, either at home or at site. β -HCG test on blood will be conducted at all visits until end of treatment on blood collected for laboratory tests. A urine dipstick pregnancy test will be conducted at the EoS/Follow-up Visit (if acceptable).

Urine dipstick pregnancy test kits will be provided locally for use between regular visits every 4 weeks.

A pregnancy test diary card will be dispensed at visits defined in the [Flow Chart](#).

The patient/parent(s)/legal guardian will be instructed on how it should be used to support the record of the date and result of urine pregnancy test(s) between consecutive visits.

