6.2.2 Treatment period(s)

Visit 2:

If for any reason the screening phase for an individual patient lasts for more than 6 weeks, then the laboratory examination for Visit 1 has to be repeated before assignment of study treatment. The screening phase (from informed consent until Visit 2) must be no longer than 12 weeks.

[figure not shown]
[figure not shown]
Detailed procedures and assessment to be performed at Visit 2 are described in [Flow Chart](#) and [Section 5](#).

Visit 2 for new patients

The following prerequisites must be met:

- Confirmation of fibrosing ILD based on HRCT central review (and biopsy central review if needed).
- Safety laboratory results from blood sampling conducted at Visit 1, including haemoglobin and eGFR measurement have been provided and are available at the site.

Observations and procedures

- 
- 

- Adverse events, [REDACTED], concomitant therapy [REDACTED] since last visit will be reviewed and recorded.
- Prior to blood draw, physical examination including vital signs, weight, height (standing and sitting), and leg length will be performed; data will be recorded in source documents and entered timely into the eCRF.
- If the ECG was abnormal at Visit 1, the 12-lead ECG at rest will be repeated (if possible, prior to blood draw) and evaluated by qualified personnel at site.
- [REDACTED]
- FVC measurement will be conducted according to procedures defined (see ISF for details).
- DLCO measurement will be conducted after FVC measurement and patient's rest. DLCO will be corrected for haemoglobin (Hb) measured at Visit 1 (see [Section 5.6.4](#) for details).
- All in/exclusion criteria will be checked, and if all in-/exclusion criteria are fulfilled the patient will qualify for the treatment period of the study.
- [REDACTED]
- Blood and urine samples (safety laboratory tests, and pregnancy test on serum in female patients only) will be collected and submitted to the central laboratory.
- [REDACTED]
- If a patient is eligible for the trial, treatment assignments will be performed by using the IRT system.
- The assigned trial medication will be administered at the site.
- Medication wallets will be dispensed, patient/parent(s)/legal guardian will be properly instructed about how and when the study medication should be taken until the next visit. The patient/parent(s)/legal guardian will be properly instructed to contact the site in case of adverse events (details given in the informed consent and assent where applicable).

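### No same-day pregnancy result is required before a new patient's first nintedanib dose; that dose rests on a Visit 1 result up to 28 days old by default

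*Protocol*

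**What the plan says.** Four parts of the protocol set the sequence at Visit 2 for new patients and those handled as new.

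- **The test.** Flow Chart footnote 13: "Pregnancy blood test will be conducted at each scheduled visit until EoT". The new-patient Visit 2 list in 6.2.2 makes it a central serum test: "pregnancy test on serum in female patients only) will be collected and submitted to the central laboratory". Section 5.2.3 agrees: "All analyses will be performed by a central laboratory", and the β-HCG "test on blood will be conducted at all visits until end of treatment on blood collected for laboratory tests".
- **When the result arrives.** The note under exclusion criteria 1 to 3 in 3.3.3: "Visit 2 laboratory results will be available only after the visit".
- **When the dose is given.** Section 4.1.4: "The first dose of trial medication should be taken during the Visit 2 in the morning at the clinic".
- **Dipstick supply.** Footnote 13: "from Visit 3 for new patients and for roll-over patients < 26 weeks, urine dipstick pregnancy tests will be provided".

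A Visit 1 result is required. Visit 1 includes a central serum pregnancy test (6.2.1), pregnancy is exclusion criterion 15 (3.3.3), and 6.2.1 wants all results that decide eligibility in hand before Visit 2. Section 6.2.2 makes the Visit 1 safety laboratory results at the site a prerequisite for Visit 2, and Table 5.2.3:1 lists serum HCG among those tests.

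The Visit 1 to Visit 2 interval should be at most 28 days but may be longer within a 12-week screening period (footnote 1). Footnote 12 has the Visit 1 safety laboratory tests repeated if that interval exceeds 6 weeks.

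**The concern.** Section 4.2.2.3 describes a high potential for teratogenicity and embryotoxicity. Section 1.2 reports embryo-foetal lethality in rats at exposures comparable to, or below, those in humans. Table 1.4.2:1 names pregnancy testing as a mitigation for foetal harm. Yet the test nearest the first dose is read only after that dose has been taken.

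A patient who conceived after the Visit 1 test, or so shortly before it that the test could not yet turn positive, can start nintedanib and continue until the central result is back. Section 3.3.4.1 then requires immediate interruption, but exposure has already begun.

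The contraception rule leaves a narrow opening of the same kind. It starts 28 days before treatment, which under the default schedule can coincide with Visit 1. A conception just before that date might be missed at Visit 1 and show only in the Visit 2 sample.

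**Working it through.** **1. Can the Visit 2 result precede the dose?** The sample goes to the central laboratory (5.2.3, 6.2.2) and the dose is taken during the visit (4.1.4). The statement that Visit 2 results come afterwards was written for liver, bilirubin and renal criteria, but the pregnancy test uses the same blood draw and the same laboratory. No visible entry in the Flow Chart, footnote 13 or the Visit 2 list asks for an on-site test first. Some Visit 2 entries are blacked out, so this rests on the visible text.

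**2. Age of the last known result at first dose.**
- Default: 4 × 7 = 28 days at most (footnote 1).
- Extended screening, if the footnote 12 repeat includes the pregnancy test: 6 × 7 = 42 days before a repeat is due.
- Section 6.2.2 counts the six weeks over the screening phase, which it dates from consent. If consent precedes Visit 1 by c days, the limit is 42 − c. This exceeds 28 only when c < 14.
- If footnote 13's opening four-weekly interval covers screening, a repeat is due after 28 days and the longer figures fall away.
- If the repeat does not include the pregnancy test and the four-weekly interval does not cover screening, only the screening limit remains: 12 × 7 = 84 days.

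The documents do not settle which reading is meant. Table 5.2.3:1 puts serum HCG among the safety laboratory tests, while the Flow Chart has separate rows for safety laboratory and pregnancy tests. Footnote 13 opens with a four-weekly interval and no restriction by period, but later has home or local urine testing "every 4-6 weeks if applicable, between clinic visits until the end of the trial". Section 5.2.3 and the intermediate-test paragraph in 6.2.2 tie the four-weekly interval to treatment and follow-up. No visit or dipstick supply between Visits 1 and 2 puts it into practice.

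**3. Exposure before the result.** Dosing is twice daily. Turnaround is not given; assuming 1 to 7 days, 2 × 1 = 2 to 2 × 7 = 14 doses.

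**4. Patients concerned.** Section 3.3 expects 20 to 30 new patients.
- Female, assuming half: 10 to 15. At 40% to 60%: 0.4 × 20 = 8 to 0.6 × 30 = 18.
- Post-menarchal, assuming half of those: 5 to 7.5, so about 5 to 8. At 30% to 70%: 0.3 × 8 = 2.4 to 0.7 × 18 = 12.6, so about 2 to 13.

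**5. Rough size of the risk.** Criterion 3 sets a method failure rate below 1% per year. Taking the highest count, 1% as an upper value, and no credit for the barrier method:
- 13 × 0.01 × 28/365 = 0.010 expected pregnancies in the whole trial.
- 13 × 0.01 × 42/365 = 0.015.

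This assumes consistent, correct use. It leaves out conceptions just before Visit 1 and poorer adherence, both of which would raise it.

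**6. Is entry still open?** The end of trial falls at about 156 weeks for the last roll-over patient and new patients are expected to have at least 76 weeks, so the last new entry is about 156 − 76 = 80 weeks after the last roll-over patient's first dose. If the 18-month recruitment period had begun by Amendment 1 (05 Aug 2022, assumption), it ended by about 05 Feb 2024, before version 6.0 (27 Nov 2024). Version 6.0 does not say that entry has closed, and 3.1 still describes it as open.

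**The case against.** The strongest reply is that the existing scheme is defensible. A negative central serum test within 28 days, abstinence or dual contraception, a repeat serum test on the day of first dose and immediate interruption if it is positive form a coherent set of safeguards. The expected number of pregnancies under correct contraceptive use is around 0.01, and the last new patient may already have been dosed. All of this stands. It limits the priority of the change but does not supply a result on the day of dosing.

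A reader might infer that no pregnancy result at all is needed before the first dose. The documents do not support that: criterion 15, the 6.2.1 rule on eligibility results and the 6.2.2 prerequisite together require the Visit 1 result. Section 8.3.1 accepts documented verbal feedback as evidence of eligibility in general, but that does not displace the 6.2.1 rule.

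A reader might also take 42 days as the plan's stated limit. It is only one reading. The Amendment 5 description says the testing interval was harmonised to every four weeks in all countries, so the four-to-six-week phrase in footnote 13 may be leftover wording, which favours the 28-day reading.

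**Conclusion.** The point holds in a narrow form. For new patients and those handled as new, the visible plan requires no pregnancy result from the day of the first dose. That dose rests on the required Visit 1 result, up to 28 days old by default. An age of 29 to 42 days is possible only in extended screening, only on the conditions set out in step 2 and, under the 6.2.2 counting rule, only if consent came less than 14 days before Visit 1. How many patients have extended screening is not given.

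The absolute risk is small, resting on perhaps 5 to 8 post-menarchal new patients under assumed proportions. The possible harm is serious and the remedy is simple, so this is worth doing as a low-cost safety improvement. The plan contains no error here. If new entry has closed, the change has no effect in this trial.

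Roll-over patients likewise have no required same-day result, but most continue nintedanib. Their first doses are probably past: the planned interim analysis followed their 52-week visit (7.2.8), and the SAP history table refers to rules already applied for the interim report.

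**What to change.** In footnote 13 and the new-patient Visit 2 list in 6.2.2, require a negative urine dipstick, read on site, before the first dose, using the urine already collected at that visit. Where urine testing is not accepted, require a local blood test with a known result. Keep the central serum test as it is. The age of the latest known result at first dose then falls from at most 28 days to 0 where the dipstick is used.

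The cost is one dipstick per female patient, site stock at Visit 2 rather than from Visit 3, a local blood test in some places, and a few lines of wording. A false-positive dipstick would briefly delay the first dose until the serum result is back. Confirm first whether any new patient can still enter.
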